## 9. STUDY CALENDAR

	Pre- Study a	Day 1 of Each Cycle b (+/- 3 days)	Every 12 weeks (+/- 1 week)	End of Treatment Visit g	Follow Up Visits f (Every 6 months +/- 1 month)
Informed Consent	X				
History and Physical c	X	X		X	
ECOG Performance Status	X	X		X	
Vital Signs d	X	X		X	
Hematology e	X	X		X	
Serum Chemistry f	X	X		X	
Liver Function Test g	X	X		X	
Coagulation Factors h	X				
EKG	X				
Serum Testosterone	X				
Research Labs i	X	X	X	X	
PSA j	X	X		X	X
CT/MRI k	X		X		
Bone Scan l	X		X		
Distribution m		X			
Compliance Assessment		X			

CONFIDENTIAL

This document is confidential. Do not disclose or use except as authorized.

**Enzalutamide for Castration-Resistant Prostate Cancer**  
**August 4, 2016**

Prior and Concomitant Medications	X	X			
Adverse Events n	X	X		X	
Tumor Biopsy o	X			X p	

- a: Baseline evaluations are to be conducted within 30 days prior to registration. Scans must be done within 60 days prior to registration. All baseline screening should be done prior to registration.
- b: A cycle will be defined as 28 days.
- c: Physical examination should include general description of participant, head, eyes, ears, nose, and throat, chest, abdominal, extremities, neurologic, skin, and lymph node examination. Any other evaluation is up to the discretion of the practitioner. It will not be considered a violation if the exam is not described as outlined here.
- d: Vital signs included upright blood pressure, heart rate, respiratory rate, body temperature and weight.
- e: Hematology testing to include WBC, ANC, hemoglobin, and platelet count.
- f: Serum chemistry to include sodium, potassium, chloride, bicarbonate, BUN, creatinine, glucose, calcium, albumin, magnesium.
- g: LFTs to include AST, ALT, alkaline phosphatase, total bilirubin and direct bilirubin.
- h: Coagulation factors to include PT, PTT, and INR.
- i: Research labs to include a blood sample for germline DNA/RNA analysis, serum hormones (to include DHEA, DHEA-S, androstenedione, testosterone, DHT), a blood sample for circulating tumor DNA analysis, a blood sample for CTC analysis. Blood for germline DNA/RNA will be collected at pre-study visit. Hormone levels will be collected at pre-study visit, every 12 weeks on study, at off-study. CTCs will be collected at pre-study visit, Day 1 of each cycle, and off study. Pre-study and off study CTC samples will be shipped overnight. CTCs collected on Day 1 of each cycle will be processed (buffy coat) and stored for delivery. Circulating tumor DNA will be collected at pre-study visit, every 12 weeks on study, at off-study.
- j: If a digital rectal examination is performed, PSA must be sampled prior to the examination. For patients enrolling for PSA progression, this is defined as a rise in PSA on two successive determinations at least one week apart and PSA levels  $\geq 2$  ng/ml (only the screening PSA needs to be  $\geq 2$  ng/ml).
- k: If baseline CT chest does not demonstrate prostate cancer, do not need to be repeated on study unless the investigator suspects new findings based on clinical signs/symptoms.
- l: For DFCI participants only, one bed position of quantitative SPECT/CT will be performed as an imaging substudy concurrently with the standard of care bone scans at baseline and at the time of the first two follow up standard of care bone scans. The field of view will be determined by the nuclear medicine physician depending on the location of the lesions on the planar images.
- m: Study agent is enzalutamide. Subjects will be continued on LHRH agonist/antagonist as prescribed. Subjects will begin taking study agent on Day 1/Cycle 1.
- n: AEs should be collected from the date informed consent is signed until 30 days after discontinuation from the study.
- o: Tumor biopsy must be performed prior to starting study medication. Participants will need to be screening and registered before having a biopsy. Friday should be avoided due to difficult of processing bone biopsies on the weekend. For DFCI participants, if the biopsy site (baseline and progression) is a pelvic bone both an aspirate and core biopsy will be obtained.
- p: Participants who stop the protocol therapy before receiving four cycles of enzalutamide will not be asked to undergo the second biopsy. The tumor biopsy at the end of the study can be done +/- 14 days of the determination of progression. Enzalutamide will be discontinued following completion of the second biopsy. Situations where the participant stops protocol therapy for reasons other than progression after receiving four cycles of enzalutamide should be discussed with the PI if it felt that the biopsy would not represent progressive disease.
- q: The End of Treatment Visit will be the visit at which it is determined that the patient will no longer be taking treatment given disease progression, toxicity, or other reason.
- r: Follow up Visits: Participants will be followed for up to 5 years post-study discontinuation or until death, whichever comes first. Participant follow up visits will be at the research clinic for the first 2 years of follow-up. Following the first 2 years, participant follow-up can be done via medical record review and/or by phone. Participants will be followed for subsequent lines of therapy, including line of agent, name of agent, and PSA kinetics following study drug discontinuation and correlate with response to study drug. This information will be updated every 6 months. The research team will collect this information during patient clinic visits, by phone, or via medical record review.

CONFIDENTIAL

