#### **Rational for Using Enzalutamide in Prostate Cancer**

First generation antiandrogens, including bicalutamide, nilutamide, and flutamide, are reversible inhibitors of the AR and have a several-fold lower affinity to the AR compared with androgens. These agents have been used in the management of advanced prostate cancer for decades. Addition of an antiandrogen at the time of CRPC has been shown to lower PSA by 50% or more in approximately one-quarter of patients. There is no data supporting the superiority of one antiandrogen over another, however nilutamide has been shown to induce PSA declines in men who have developed resistance to AR inhibition with flutamide or bicalutamide.

It was first noted in the early 1990s that disease progression, despite the combination of an LHRH (luteinizing hormone-releasing hormone) agonist and an antiandrogen, could be stopped and reversed simply through discontinuation of the antiandrogen. Stopping the antiandrogen in men with a rising PSA, termed antiandrogen withdrawal, can result in PSA declines in between 10-20% of men. Further work demonstrated that in the setting of AR overexpression or mutation, conventional antiandrogens have the potential to exhibit paradoxical partial agonist activity, promoting prostate cancer progression. Thus, more potent antagonists lacking agonist activity are necessary.

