#### 3.1 Eligibility Criteria

Participants must meet the following criteria on screening examination to be eligible to participate in the study:

- 3.1.1 Be a male  $\geq 18$  years of age.
- 3.1.2 Participants must have histologically or cytologically confirmed adenocarcinoma of the prostate without  $\geq 50\%$  neuroendocrine differentiation or small cell histology.
- 3.1.3 Participants must have progressive disease as defined by either:
  - Castrate resistant disease as defined by PCWG. Participants must have a rise in PSA on two successive determinations at least one week apart and PSA levels  $\geq 2$  ng/ml (only the screening PSA needs to be  $\geq 2$  ng/ml) and testosterone levels  $< 50$  ng/dL, OR
  - Soft tissue progression defined by RECIST 1.1, OR
  - Bone disease progression defined by PCWG2 with two or more new lesions on bone scan.
- 3.1.4 Participants must have a testosterone levels  $< 50$  ng/dL.
- 3.1.5 CRPC with metastatic disease with at least one site of metastatic disease must be amenable to needle biopsy. Soft tissue biopsy sites include: lymph node or visceral metastases. Bone sites include lumbar vertebrae, pelvic bones and long bones. Excluded sites are thoracic, cervical vertebrae, skull and rib lesions. Biopsy site will be selected with guidance of interventional radiologist determining best site to optimize balance of obtaining useful tissue for analysis and minimizing risk.
- 3.1.6 Participants without orchiectomy must be maintained on LHRH agonist/antagonist therapy.

CONFIDENTIAL

This document is confidential. Do not disclose or use except as authorized.

- 3.1.7 Participants may have had any number of previous hormonal therapies (antiandrogens, estrogens, finasteride, dutasteride, ketoconazole, abiraterone) provided these were discontinued  $\geq 4$  weeks before enrollment. Participants on prednisone 10 mg daily or another equivalent steroid dose are eligible. Participants on inhaled steroids are eligible.
- 3.1.8 Participants may have had up to two previous cytotoxic therapeutic regimens provided these were discontinued  $\geq 4$  weeks before enrollment. The use of antineoplastic agents for non-cancer therapy (i.e. colitis, rheumatoid arthritis) may be allowed provided the patient has been on a stable dose without toxicities greater than grade 1.

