### 10.2 Other Response Parameters

Descriptive statistics (including mean, standard deviation (SD), minimum, maximum, median, interquartile range) will be provided on levels of serum hormones and changes from baseline.

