**Number of Subjects/Study Duration:**

We plan to enroll a total of 66 participants to obtain 40 evaluable participants. Assuming an accrual rate of 6 participants per month, enrollment will take 11 months. Participants will be treated with enzalutamide 160 mg orally per day. We will assess PSA at baseline and day 1 of each 28-day cycle until radiographic progression defined by PCWG2. Participants will continue on therapy until radiographic or symptomatic progression or taken off study for another reason.

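### The only pre-treatment serum hormone and ctDNA samples can fall inside the washout from prior hormonal therapy, and the reference value for PSA response is not named

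*Combined protocol and SAP*

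**What the plan says.** **Baseline window.** Section 9, footnote a: "Baseline evaluations are to be conducted within 30 days prior to registration". It adds: "All baseline screening should be done prior to registration".

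**Washout.** Section 3.1.7: "Participants may have had any number of previous hormonal therapies (antiandrogens, estrogens, finasteride, dutasteride, ketoconazole, abiraterone) provided these were discontinued" 4 weeks or more before enrollment. Section 3.1.9 sets the same interval for other prostate cancer treatment, apart from LHRH agonists or antagonists, bisphosphonates and denosumab. Both count to enrollment, not to the baseline sample. The plan does not say whether enrollment and registration are the same date.

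**Sampling.** Section 9, footnote i: "Hormone levels will be collected at pre-study visit, every 12 weeks on study, at off-study". ctDNA follows the same schedule. CTCs are taken pre-study, on Day 1 of every cycle and off study. For PSA, Section 14.1 (Number of Subjects/Study Duration) says: "We will assess PSA at baseline and day 1 of each 28-day cycle".

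**Use of the values.** Change in serum androgens is the first secondary objective (Section 1.3). Section 10.2 says descriptive statistics "will be provided on levels of serum hormones and changes from baseline". Section 14.2 compares markers between PSA responders and non-responders, and calls these analyses exploratory.

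**A second baseline rule.** Section 10.1.3 limits all baseline evaluations to the 4 weeks before treatment starts.

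**The concern.** The baseline window is 2 days longer than the minimum washout, and the two are counted independently. A man can therefore give his baseline blood while an earlier drug is still wearing off.

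For serum hormones and ctDNA that sample is the only pre-treatment one. If the earlier drug had lowered his androgens, their recovery would appear as a rise on enzalutamide. The plan also studies androgen levels in tumor and serum in connection with resistance and response, so such a rise could be misread.

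For PSA, Section 2.1.1 says that stopping an antiandrogen "can result in PSA declines in between 10-20% of men". If the pre-study PSA is the reference, such a fall could be credited to enzalutamide and could place a man in the wrong group for the comparison in Section 14.2.

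**Working it through.** The plan gives no figure for this point, so the check is date arithmetic.

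**Inputs.** Baseline window: 30 days before registration (Section 9, footnote a). Minimum washout: 28 days before enrollment (3.1.7, 3.1.9). Competing limit: 28 days before treatment (10.1.3). Registration to first dose: should be within 5 days at other participating institutions (4.3); no limit is stated for DF/HCC sites (4.1). Assumption: enrollment is the registration date.

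**1. Overlap.** Let a man stop prior therapy *w* days before registration (*w* ≥ 28) and give baseline blood *d* days before registration (0 ≤ *d* ≤ 30). The draw is *w* − *d* days after his last dose.
- With *w* = 28, this runs from 28 − 30 = −2 days (still on drug) to 28 − 0 = 28 days.
- A draw at least 28 days after the last dose is guaranteed only if *w* ≥ 28 + 30 = 58. Men who stopped 28 to 57 days before registration are exposed.

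**2. If Section 10.1.3 governs.** Let the first dose come *g* days after registration. The earliest draw is then *g* − 28 days relative to registration, and the latest permitted stop is −28. The earliest draw is therefore *g* days after the last prior dose: 0 days for a same-day start, 5 days for *g* = 5. Sampling on drug disappears; sampling just after stopping remains.

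**3. Conflict between the two rules.** Footnote a allows 30 + *g* days from draw to first dose: 30 for *g* = 0 and 35 for *g* = 5. That is 2 and 7 days beyond the limit in 10.1.3.

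**4. Which samples are exposed.**

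| Sample | Pre-study | Cycle 1 Day 1 | Gap |
|---|---|---|---|
| Serum hormones | Yes | No | Only pre-treatment value can fall in washout |
| ctDNA | Yes | No | Same |
| PSA | Yes | Yes | Reference value not named |
| CTCs | Yes, shipped overnight | Yes, stored as buffy coat | Two pre-dose samples, handled differently |
| Tumor biopsy | After registration (footnote o) | – | None from this window |

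**5. Hormones, illustration only.** The documents give neither the effect of the earlier drugs on serum androgens nor the share of men who stopped near the limit. Assume no true change on enzalutamide, and a baseline suppressed by a fraction *s* in a share *f* of men. The spurious mean percent change is *f* × *s*/(1 − *s*):

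| Assumed *s* | *f* = 10% | *f* = 25% | *f* = 50% |
|---|---|---|---|
| 25% | +3.3% | +8.3% | +16.7% |
| 50% | +10% | +25% | +50% |
| 75% | +30% | +75% | +150% |

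Section 10.2 does not say whether change is absolute or percent; the table applies to percent change.

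**6. PSA.** The spurious share is the share who had just stopped an antiandrogen times the withdrawal rate of 10–20% (2.1.1). With an assumed share of 10–50%, this is 0.10 × 0.10 = 1% to 0.50 × 0.20 = 10% of participants, or 66 × 0.01 = 0.7 to 66 × 0.10 = 6.6 men. It is an upper range: Section 2.1.1 does not give the depth of the fall, and the calculation treats every such baseline as drawn before the fall.

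**7. Design figures.** The noncentral t distribution reproduces the plan's power: paired test with 40 pairs, 80% at 0.454 SD and 90% at 0.526 SD; 10 against 30 at 1.05 SD, 80%. The yield is 0.95 × 0.90 × 0.70 = 0.5985, or 39.5 of 66. None of these depends on the baseline window.

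**The case against.** **Section 10.1.3 already limits the window.** It speaks of all baseline evaluations, and the same section covers PSA recording. The biopsy must follow registration and precede the first dose, so a draw 28 or more days before registration would meet the limit only if registration, biopsy and dosing shared one day. This stands against sampling on drug. It does not close the gap, because a draw 0 to 5 days after the last prior dose would still comply. It is also unclear that a section on disease evaluation governs research hormone and ctDNA tubes.

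**Sampling on drug is a narrow case.** A reader might infer that baselines will commonly be on-treatment values. The margin is 2 days, it needs enrollment to mean registration, and consent must be given while the man is still on the earlier drug (Section 13.2). Sampling soon after stopping is the main exposure.

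**PSA and CTCs have Day 1 draws.** This stands. A pre-dose value after washout is scheduled for both. For PSA the remaining gap is that Section 14.1 lists baseline apart from Day 1 and nothing says which one is the reference. Section 14.2 defers to PCWG2 for PSA response, and that source cannot be consulted here. For the same reason it cannot be shown that the qualifying PSA rise in 3.1.3 may precede antiandrogen withdrawal.

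**The endpoints are not primary.** This also stands. Hormone change is secondary and descriptive, ctDNA is exploratory, and the tissue for the primary analysis is taken after registration.

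**Conclusion.** The gap is real and limited. As written, the only pre-treatment serum hormone and ctDNA samples can be drawn during washout, from 2 days before to 28 days after the last prior dose for a man who stopped exactly 4 weeks before registration. If Section 10.1.3 applies, the earliest draw moves to 0 to 5 days after that dose. Change from baseline in serum androgens can therefore be biased.

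A reader might conclude that it is biased, or by a particular amount. The documents do not support that: they give neither the share of men near the limit nor the effect of the earlier drugs on androgens, and the hormone table rests wholly on assumed values.

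For PSA, up to 1–10 percentage points of participants could show a withdrawal fall, under the assumed 10–50% share and only if the pre-study value is the reference. It is tempting to set this against the 25% response rate in Section 14.2. That rate only illustrates power among 40 evaluable men; the trials described in Section 2.1.1 report 54–56%. Nor does the documented withdrawal rate show how many falls would count as responses.

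The primary paired-biopsy analysis, sample size and power are unaffected.

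**What to change.** 1. In Section 9, footnotes a and i, take the baseline serum hormone and ctDNA samples on Cycle 1 Day 1 before the first dose, and exempt them from the rule that baseline work precedes registration. With enrollment taken as registration, every such baseline is then at least 28 days after prior therapy.
2. In Sections 10 and 14.2, define the pre-dose Cycle 1 Day 1 PSA as the reference for PSA response. Keep the screening PSA for eligibility.
3. Reconcile the 30-day window in footnote a with the 4-week limit in Section 10.1.3, say which evaluations each covers, and state whether enrollment means registration.
4. In Section 10.2, add a sensitivity analysis of hormone change by recent prior therapy, using the prior-medication data already collected.
5. Leave the CTC baseline at the pre-study visit unless Day 1 handling is matched to it. Pre-study and off-study CTC samples are both shipped overnight, and a Day 1 baseline stored as buffy coat would break that match.

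**Cost.** Calendar wording and one short analysis. Blood is already drawn on Day 1 of each cycle, so the tubes move and do not increase in number. The downside is that a man registered but never dosed has no research baseline sample. This loss is small: Section 4.1 cancels such registrations at DF/HCC sites, and Section 4.3 allows cancellation elsewhere.

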## 5. TREATMENT PLAN

All protocol required therapy will be prescribed by prescription and taken by the participant on an outpatient basis. A baseline metastasis biopsy will be done prior to starting protocol therapy.

Participants will be treated with four 40 mg capsules (160 mg) once daily of enzalutamide taken orally. All participants without orchiectomy will be maintained on LHRH agonist/antagonist therapy. Participants will be evaluated clinically and with laboratory studies on day 1 of every 28 day cycle. Participants will maintain a drug diary from time of initiation of study treatment to time of discontinuation from the study (Appendix C). Participants will be continued on therapy until evidence of symptomatic or radiographic progression or taken off study for another reason.

A metastasis biopsy will be performed while the participant is still on enzalutamide at the time of progression. For DFCI participants, if the biopsy site (baseline and progression) is a pelvic bone both an aspirate and core biopsy will be obtained. After progression biopsy is performed, protocol therapy will be discontinued. Participants who stop protocol therapy before receiving four cycles of enzalutamide will not be asked to undergo a second biopsy. The tumor biopsy at the end of study is otherwise mandatory and can be done +/- 14 days of determination of progression. Situation where the participant stops protocol therapy for reasons other than progression after receiving 4 cycles of enzalutamide should be discussed with the PI if it is felt that biopsy would not represent progressive disease. For DFCI participants, quantitative SPECT/CT imaging substudy will be performed in addition to standard bone scanning at baseline and at the time of the first two follow up bone scans.

Expected toxicities and potential risks as well as dose modifications for enzalutamide are described in Section 6 (Expected Toxicities and Dosing Delays/Dose Modifications). No investigational or commercial agents or therapies other than those described below may be administered with the intent to treat the participant's malignancy.

Treatment Description					
Agent	Pre-medications; Precautions	Dose	Route	Schedule	Cycle Length
Enzalutamide	Can be taken with or without food. The capsules should be swallowed whole with water. Do not chew, dissolve, or open capsules.	160 mg	Oral	Once daily	28 days (4 weeks)

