## **11.8 Monitoring of Adverse Events and Period of Observation**

All AEs, both serious and non-serious, and deaths that are encountered from initiation of study intervention, throughout the study, and within 30 days of the last study intervention should be followed to their resolution, or until the participating investigator assesses them as stable, or the participating investigator determines the event to be irreversible, or the participant is lost to follow-up. The presence and resolution of AEs and SAEs (with dates) should be documented on the appropriate case report form and recorded in the participant's medical record to facilitate source data verification.

For some SAEs, the study sponsor or designee may follow-up by telephone, fax, and/or monitoring visit to obtain additional case details deemed necessary to appropriately evaluate the SAE report (e.g., hospital discharge summary, consultant report, or autopsy report).

Participants should be instructed to report any serious post-study event(s) that might reasonably be related to participation in this study. Participating investigators should notify the DF/HCC Overall PI and their respective IRB of any unanticipated death or AE occurring after a participant has discontinued or terminated study participation that may reasonably be related to the study.

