#### **12.1.2 Data Submission**

The schedule for completion and submission of case report forms (paper or electronic) to the ODQ is as follows:

CONFIDENTIAL

This document is confidential. Do not disclose or use except as authorized.

Form	Submission Timeline
Eligibility Checklist	Complete prior to registration with ODQ.
On Study Form	Within 14 days of registration.
Baseline Assessment Form	Within 14 days of registration.
Treatment Form	Within 10 days of the last day of the cycle.
AE Report Form	Within 10 days of the last day of the cycle. If AEs are ongoing at the end of the last cycle, continue to submit AE reports until resolution or 30 days post-treatment.
Response Assessment Form	Within 10 days of the completion of the cycle required for response evaluation.
Off Treatment/Off Study Form	Within 14 days of completing treatment or being taken off study for any reason.
Follow up/Survival Form	Within 14 days of the protocol defined follow up visit date or call.

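### The last scheduled AE assessment can come up to 14 days before the second biopsy and last dose, and no AE contact is scheduled in the 30 days that follow

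*Combined protocol and SAP*

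**What the plan says.** The Study Calendar (section 9) marks adverse events at Pre-Study, Day 1 of each cycle and the End of Treatment Visit. The Follow Up Visits column ("Every 6 months +/- 1 month") has no mark in that row; its only mark is PSA.

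Three statements fix the order of events at the end of treatment:

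- Note q: "The End of Treatment Visit will be the visit at which it is determined that the patient will no longer be taking treatment", whether for progression, toxicity or another reason.
- Note p: "The tumor biopsy at the end of the study can be done +/- 14 days of the determination of progression", and "Enzalutamide will be discontinued following completion of the second biopsy".
- Section 5: "The tumor biopsy at the end of study is otherwise mandatory and can be done +/- 14 days of determination of progression". Participants who stop before four cycles are not asked for it.

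Five places bear on when AE collection ends:

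- Section 6: at the final study visit.
- Note n: "AEs should be collected from the date informed consent is signed until 30 days after discontinuation from the study".
- Section 11.4.1: 30 days after the last dose, for SAEs and listed graded events.
- Section 11.8: AEs of any seriousness encountered up to and "within 30 days of the last study intervention should be followed to their resolution", or until they are stable, irreversible or the participant is lost.
- Section 12.1.2, on the AE form: "If AEs are ongoing at the end of the last cycle, continue to submit AE reports until resolution or 30 days post-treatment".

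**The concern.** The plan sets a 30-day period for collecting AEs after treatment but schedules nothing inside it at which anyone asks about them. For a participant who progresses, the last scheduled question about AEs can also come before two things that may cause them: an invasive biopsy done for research, and the final days of dosing.

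Section 11.1.1 counts events after any protocol procedure as AEs, and safety and tolerability is a secondary objective (section 1.3). Late treatment-related events could be under-counted in the section 14.2 toxicity summary. Delayed biopsy events such as bleeding, infection or pain could be under-counted in AE reporting. Because the end of collection is defined in several ways, two sites could follow the protocol and still stop collecting on different dates.

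**Working it through.** No plan figure describes this gap, so the check is a day count, a ceiling on numbers and a calculation of remaining drug.

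**1. Day count.** Take the End of Treatment Visit as day 0 and assume progression is determined at that visit.

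- Second biopsy (note p; section 5): day -14 to day +14.
- Last dose: after the biopsy, so as late as about day 14.
- End of 30 days from last dose or last intervention (11.4.1, 11.8): as late as 14 + 30 = day 44.
- First follow-up at 6 months +/- 1 month: 5 x 30.44 = about 152 days at the earliest, 6 x 30.44 = about 183 nominally, 7 x 30.44 = about 213 at the latest.

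Even if follow-up is counted from day 0, its earliest date is 152 - 44 = 108 days after the latest close of the window. The 44 days is a maximum. If the biopsy and last dose fall on day 0 there is no lag, but the following 30 days still contain no scheduled AE contact.

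**2. How many participants.** Section 14.1 assumes 95% eligible, 90% of these with paired biopsies and 70% with evaluable tumors. Its yield reproduces: 0.95 x 0.90 x 0.70 = 0.5985, and 66 x 0.5985 = 39.5, the planned 40. Without the tumor-evaluability factor, 66 x 0.95 x 0.90 = 56.4, so about 56 participants have a second biopsy. This caps the number whose visit can precede that biopsy. The documents do not give the share biopsied after the visit.

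**3. Drug remaining at day 30 after the last dose.** Fraction = 2^(-30/half-life), with the terminal half-life in section 7.1.3 of 5.8 days (range 2.8 to 10.2):

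- 2.8 days: 0.06%
- 5.8 days: 2.8%
- 10.2 days: 13.0%

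For N-desmethyl enzalutamide the section gives 7.8 to 8.6 days, from healthy volunteers after a single dose: 7.0% to 8.9%. At day 14 the parent drug figures are 3.1%, 18.8% and 38.6%. Exposure therefore runs into the unscheduled period, by an amount that varies widely between participants. This has no bearing on biopsy events.

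**4. Other capture routes, for an event that starts after the visit.**

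- 11.2: AEs are assessed at participant evaluation time points; none is scheduled in the 30 days.
- 11.4.1: the 24-hour clock starts when the site learns of the event.
- 11.8: applies to AEs that are encountered, and asks participants to report serious, possibly related post-study events.
- Section 6: contact is optional and limited to toxicity continuing at the off-study visit.
- 5.6: participants removed for unacceptable AEs stay on study until resolution.
- 12.1.2: after the last cycle, the form continues for AEs already ongoing.

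None of these schedules a question about a new non-serious event.

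**The case against.** The best defence is that the duty to collect already exists. Note n is attached to the AE row itself, so collection does not end at the End of Treatment Visit. Section 11.2 requires every AE to be recorded however it is detected. Section 11.8 covers serious and non-serious events and also has investigators report unanticipated, possibly related AEs after discontinuation. Section 12.1.2 is a submission timetable rather than a collection rule. A participant still taking drug between the visit and the biopsy is plausibly still in a cycle, so the AE form would cover that interval. The biopsy is marked in the End of Treatment column, may precede the visit, and is itself an in-person contact.

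All of this stands, and it rules out some stronger readings. A reader might infer that late events will be lost, or that participants' own reports of serious events are the only safeguard. The documents support neither. A reader might also infer that 11.4.1 promises coverage of all AEs; it concerns SAEs and listed graded events.

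Nor would biopsy events necessarily vanish from the section 14.2 table or from the monitoring committee's data. The table is limited to treatment-related toxicity, with attribution to study treatment (11.1.4), so most biopsy events would not enter it even if recorded. Section 12.2 lists what the committee may receive, such as unexpected AEs of grade 2 or higher, and does not name minor expected biopsy events.

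What the defence does not supply is an occasion on which the duty is carried out. A duty to record what is detected finds less than a scheduled question does.

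**Conclusion.** The point holds in limited form. Following the calendar as written, the last marked AE assessment can precede the second biopsy and last dose by up to 14 days, and no AE contact is scheduled before about month 5. New non-serious AEs after the visit rely on unscheduled reporting and may be missed. New SAEs have a reporting route, but it works only once the site knows of them. The likely effect is some under-counting of late treatment-related events in the 14.2 summary, and of biopsy events mainly in AE reporting.

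The sizes are ceilings: 44 days, and about 56 participants with a second biopsy. They assume that the visit falls on the day progression is determined, that the biopsy uses the full 14 days, and that the section 14.1 yield is met. The number of events missed cannot be estimated from the documents. The primary tissue analysis is unaffected. Separately, the statements on when AE collection ends do not agree and must be reconciled, whatever the size of the gap.

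**What to change.** - Schedule one AE contact about 30 days after the later of last dose and second biopsy. Telephone is enough. Mark it in the AE row of the Study Calendar.
- State one AE collection end date and use it in section 6, note n, 11.4.1, 11.8 and 12.1.2.
- Reword 12.1.2 so that the AE form covers new events up to that contact, and follows ongoing events as 11.8 does.

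The cost is one call per participant by existing site staff, one calendar mark and some wording changes. Dosing, biopsy timing, eligibility and endpoints stay as they are.
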